11.10.5. Safety Tables

| Safety: | Safety: Tables | | | | | |
|---------|---|-------------------------|---|--|---------------------------|--|
| No. | Population | IDSL / Example Shell | Title | Programming Notes | Deliverable [Priority] | |
| Advers | e Events (AEs) | | | | | |
| 3.1. | Safety | AE1 | Summary of Treatment Emergent Adverse Events by System Organ Class and Preferred Term – Part 1 | The general layout of all the safety tables would follow mock shell SAFE_T4 for the column headers and order for both Part 1 and Part 2 tables. This will not include Cohort C, Part 1. | SAC | |
| 3.2. | Safety | AE1 | Summary of Treatment Emergent Adverse Events by System Organ Class and Preferred Term – Part 2 | | SAC | |
| 3.3. | Bystander Safety (Part 1, Cohort C) | AE1 | Summary of Treatment Emergent Adverse Events by System Organ Class and Preferred Term – Bystander | | SAC | |
| 3.4. | Safety | AE1 | Summary of Treatment Related Adverse Events by System Organ Class and Preferred Term – Part 1 | This will not include Cohort C, Part 1. | SAC | |
| 3.5. | Safety | AE1 | Summary of Treatment Related Adverse Events by System Organ Class and Preferred Term – Part 2 | | SAC | |
| 3.6. | Bystander Safety (Part 1, Cohort C) | AE1 | Summary of Treatment Related Adverse Events by System Organ Class and Preferred Term – Bystander | | SAC | |
| 3.7. | Safety | AE5A | Summary of Treatment Emergent Adverse Events by System Organ Class and Maximum Severity – Part 1 | This will not include Cohort C, Part 1. | SAC | |
| 3.8. | Safety | AE5A | Summary of Treatment Emergent Adverse Events by System Organ Class and Maximum Severity – Part 2 | | SAC | |

| Safety: | Safety: Tables | | | | | |
|---------|---|-------------------------|---|---|---------------------------|--|
| No. | Population | IDSL / Example Shell | Title | Programming Notes | Deliverable [Priority] | |
| 3.9. | Bystander Safety (Part 1, Cohort C) | AE5A | Summary of Treatment Emergent Adverse Events by System Organ Class and Maximum Severity – Bystander | | SAC | |
| 3.10. | Safety | AE5A | Summary of Treatment Related Adverse Events by System Organ Class and Maximum Severity – Part 1 | This will not include Cohort C, Part 1. | SAC | |
| 3.11. | Safety | AE5A | Summary of Treatment Related Adverse Events by System Organ Class and Maximum Severity – Part 2 | | SAC | |
| 3.12. | Bystander Safety (Part 1, Cohort C) | AE5A | Summary of Treatment Related Adverse Events by System Organ Class and Maximum Severity – Bystander | | SAC | |
| 3.13. | Safety | AE1 | Summary of All Serious Adverse Events – Part 1 | This will not include Cohort C, Part 1. | SAC | |
| 3.14. | Safety | AE1 | Summary of All Serious Adverse Events – Part 2 | | SAC | |
| 3.15. | Bystander Safety (Part 1, Cohort C) | AE1 | Summary of All Serious Adverse Events – Bystander | Only for Cohort C, Part 1. | SAC | |
| 3.16. | Safety | AE1 | Summary of Adverse Events Leading to Permanent Discontinuation of Study Drug or Withdrawal from the Study – Part 1 | This will not include Cohort C, Part 1. | SAC | |
| 3.17. | Safety | AE1 | Summary of Adverse Events Leading to Permanent Discontinuation of Study Drug or Withdrawal from the Study – Part 2 | | SAC | |
| 3.18. | Bystander Safety (Part 1, Cohort C) | AE1 | Summary of Adverse Events Leading to Permanent Discontinuation of Study Drug or Withdrawal from the Study – Bystander | | SAC | |
| Labora | tory: Chemistry | I | | | | |
| 3.19. | Safety | LB1 | Summary of Chemistry Changes from Baseline by Visit – Part 1 | This will not include Cohort C, Part 1. | SAC | |

| Safety: | Safety: Tables | | | | | | | |
|---------|---|-------------------------|---|---|---------------------------|--|--|--|
| No. | Population | IDSL / Example Shell | Title | Programming Notes | Deliverable [Priority] | | | |
| 3.20. | Safety | LB1 | Summary of Chemistry Changes from Baseline by Visit – Part 2 | | SAC | | | |
| 3.21. | Bystander Safety (Part 1, Cohort C) | LB1 | Summary of Chemistry Changes from Baseline by Visit – Bystander | Only for Cohort C, Part 1. | SAC | | | |
| 3.22. | Safety | LB17 | Summary of Clinical Chemistry Values by Potential Clinical Importance – Part 1 | This will not include Cohort C, Part 1. | SAC | | | |
| 3.23. | Safety | LB17 | Summary of Clinical Chemistry Values by Potential Clinical Importance – Part 2 | | SAC | | | |
| 3.24. | Bystander Safety (Part 1, Cohort C) | LB17 | Summary of Clinical Chemistry Values by Potential Clinical Importance – Bystander | Only for Cohort C, Part 1. | SAC | | | |
| Labora | tory: Hematolo | gy | | | | | | |
| 3.25. | Safety | LB1 | Summary of Haematology Changes from Baseline by Visit – Part 1 | This will not include Cohort C, Part 1. | SAC | | | |
| 3.26. | Safety | LB1 | Summary of Haematology Changes from Baseline by Visit – Part 2 | | SAC | | | |
| 3.27. | Bystander Safety (Part 1, Cohort C) | LB1 | Summary of Haematology Changes from Baseline by Visit – Bystander | Only for Cohort C, Part 1. | SAC | | | |
| 3.28. | Safety | LB17 | Summary of Hematology Values by Potential Clinical Importance – Part 1 | This will not include Cohort C, Part 1. | SAC | | | |
| 3.29. | Safety | LB17 | Summary of Hematology Values by Potential Clinical Importance – Part 2 | | SAC | | | |
| 3.30. | Bystander Safety (Part 1, Cohort C) | LB17 | Summary of Hematology Values by Potential Clinical Importance – Bystander | Only for Cohort C, Part 1. | SAC | | | |

| Safety: | Safety: Tables | | | | | | |
|---------|---|-------------------------|---|---|---------------------------|--|--|
| No. | Population | IDSL / Example Shell | Title | Programming Notes | Deliverable [Priority] | | |
| Labora | tory: Coagulati | on | | | | | |
| 3.31. | Safety | LB1 | Summary of Coagulation Changes from Baseline by Visit – Part 1 | Only for Cohorts B, Part 1. | SAC | | |
| 3.32. | Safety | LB1 | Summary of Coagulation Changes from Baseline by Visit – Part 2 | Only for Cohorts B, Part 2. | SAC | | |
| Teleme | try | | | | | | |
| 3.33. | Safety | Non-standard SAFE_T2 | Summary of Telemetry Findings – Part 1 | This will not include Cohort C, Part 1. | SAC | | |
| 3.34. | Safety | Non-standard SAFE_T2 | Summary of Telemetry Findings – Part 2 | | SAC | | |
| Spirom | etry | | | | | | |
| 3.35. | Safety | Non-standard SAFE_T3 | Summary of Spirometry Data – Part 1 | This will not include Cohort C, Part 1. | SAC | | |
| 3.36. | Safety | Non-standard SAFE_T3 | Summary of Spirometry Data – Part 2 | | SAC | | |
| ECG | | | | | | | |
| 3.37. | Safety | EG1 | Summary of ECG Findings by Visit – Part 1 | This will not include Cohort C, Part 1. | SAC | | |
| 3.38. | Safety | EG1 | Summary of ECG Findings by Visit – Part 2 | | SAC | | |
| 3.39. | Bystander Safety (Part 1, Cohort C) | EG1 | Summary of ECG Findings by Visit – Bystander | Only for Cohort C, Part 1. | SAC | | |
| 3.40. | Safety | EG2 | Summary of Change from Baseline in ECG Values by Visit – Part 1 | This will not include Cohort C, Part 1. | SAC | | |

| Safety: | Tables | | | | |
|----------|---|-------------------------|---|--|---------------------------|
| No. | Population | IDSL / Example Shell | Title | Programming Notes | Deliverable [Priority] |
| 3.41. | Safety | EG2 | Summary of Change from Baseline in ECG Values by Visit – Part 2 | | SAC |
| 3.42. | Bystander Safety (Part 1, Cohort C) | EG2 | Summary of Change from Baseline in ECG Values by Visit – Bystander | Only for Cohort C, Part 1. | SAC |
| 3.43. | Safety | Non-standard SAFE_T7 | Frequency of Maximum ECG Values by PCI Category – Part 1 | Compute and display Maximum by day. | SAC |
| 3.44. | Safety | Non-standard SAFE_T7 | Frequency of Maximum ECG Values by PCI Category – Part 2 | | SAC |
| 3.45. | Bystander Safety (Part 1, Cohort C) | Non-standard SAFE_T7 | Frequency of Maximum ECG Values by PCI Category – Bystander | Compute and display Maximum by day. Only for Cohort C, Part 1. | SAC |
| 3.46. | Safety | Non-standard SAFE_T8 | Frequency of Worst Change from Baseline Values of QTcB and QTcF by PCI Category – Part 1 | Compute and display Maximum by day. | SAC |
| 3.47. | Safety | Non-standard SAFE_T8 | Frequency of Worst Change from Baseline Values of QTcB and QTcF by PCI Category – Part 2 | | SAC |
| 3.48. | Bystander Safety (Part 1, Cohort C) | Non-standard SAFE_T8 | Frequency of Worst Change from Baseline Values of QTcB and QTcF by PCI Category – Bystander | Compute and display Maximum by day. Only for Cohort C, Part 1. | SAC |
| Vital Si | gns | | | | |
| 3.49. | Safety | VS1 | Summary of Vital Signs by Visit – Part 1 | This will not include Cohort C, Part 1. | SAC |
| 3.50. | Safety | VS1 | Summary of Vital Signs by Visit – Part 2 | | SAC |
| 3.51. | Bystander Safety (Part 1, Cohort C) | VS1 | Summary of Vital Signs by Visit – Bystander | Only for Cohort C, Part 1. | SAC |

| Safety: | Safety: Tables | | | | | | | |
|---------|---|-------------------------|---|---|---------------------------|--|--|--|
| No. | Population | IDSL / Example Shell | Title | Programming Notes | Deliverable [Priority] | | | |
| 3.52. | Safety | VS1 | Summary of Change from Baseline in Vital Signs by Visit – Part 1 | This will not include Cohort C, Part 1. | SAC | | | |
| 3.53. | Safety | VS1 | Summary of Change from Baseline in Vital Signs by Visit – Part 2 | | SAC | | | |
| 3.54. | Bystander Safety (Part 1, Cohort C) | VS1 | Summary of Change from Baseline in Vital Signs by Visit – Bystander | Only for Cohort C, Part 1. | SAC | | | |
| 3.55. | Safety | VS2 | Summary of Vital Signs by PCI – Part 1 | This will not include Cohort C, Part 1. | SAC | | | |
| 3.56. | Safety | VS2 | Summary of Vital Signs by PCI – Part 2 | | SAC | | | |
| 3.57. | Bystander Safety (Part 1, Cohort C) | VS2 | Summary of Vital Signs by PCI - Bystander | Only for Cohort C, Part 1. | SAC | | | |
| Exposu | re and Treatment | Compliance | | | | | | |
| 3.58 | Safety | Non-standard SAFE_T5 | Summary of Extent of Exposure to Study Treatment – Part 1 | This will not include Cohort C, Part 1. | SAC | | | |
| 3.59 | Safety | Non-standard SAFE_T5 | Summary of Extent of Exposure to Study Treatment – Part 2 | | SAC | | | |

| Safety: | Safety: Tables | | | | | | |
|---------|---|-------------------------|--|-------------------|---------------------------|--|--|
| No. | Population | IDSL / Example Shell | Title | Programming Notes | Deliverable [Priority] | | |
| 3.60 | Bystander Safety (Part 1, Cohort C) | Non-standard SAFE_T5 | Summary of Extent of Exposure to Study Treatment – Bystander | | SAC | | |

11.10.6. Pharmacokinetic Tables

| Pharma | Pharmacokinetic: Tables | | | | | | | |
|--------|-------------------------|-------------------------|--|---|---------------------------|--|--|--|
| No. | Population | IDSL / Example Shell | Title | Programming Notes | Deliverable [Priority] | | | |
| PK Cor | ncentration Data | a | | | | | | |
| 4.1. | Systemic PK | PK01 | Summary of CCI15106 Plasma Pharmacokinetic Concentration- Time Data [ng/mL] by Cohort and Visit | | SAC | | | |
| 4.2. | Systemic PK | PK01 | Summary of plasma CCI15106 Concentration Data at Follow Up visit [ng/mL] by Cohort | This will not include Cohort C, Part 1. | SAC | | | |
| 4.3. | BAL PK | PK01 | Summary of Lung ELF CCI15106 Concentration Data [ng/mL] by Cohort | | SAC | | | |
| PK Der | ived Parameter | S | | | | | | |
| 4.4. | Systemic PK | PK03 | Summary of Derived CCI15106 Plasma Pharmacokinetic Parameters by Cohort and Visit | This will not include Cohort C, Part 1. | SAC | | | |
| 4.5. | Systemic PK | Non-Standard PK_T1 | Summary of Assessment of Dose Proportionality (Part 1 and Part 2) | Only for Cohorts A, Part 1 and Part 2. | SAC | | | |
| 4.6. | Systemic PK | Non-Standard PK_T2 | Summary of Assessment of Steady State (Part 1 and Part 2) | This will not include Cohort C, Part 1. | SAC | | | |
| 4.7. | Systemic PK | Non-Standard PK_T3 | Summary of Assessment of Accumulation (Part 1 and Part 2) | For Cohort A, Cohort B, Part 1, and Cohort B, Part 2. | SAC | | | |

11.10.7. Pharmacokinetic Figures

| No. | Population | IDSL / Example Shell | Title | Programming Notes | Deliverable [Priority] |
|--------|----------------|-------------------------|--|--|---------------------------|
| Mean/N | ledian Concent | tration Plots | | | |
| 4.1. | Systemic PK | PK17 | Mean (+SD) CCI15106 Plasma Concentration-Time Plot (Linear and Semi-log) (Part 1) | For Part 1, Overlay all cohorts and doses on same page, plot time upto 1) 72 hours post dose 2) 12 hours post dose [excluding the data after the 2 nd dose following the BD doses for both 1] & 2] to see better the earlier timepoitns. 3) plot to overlay day 1 and day 14 after the 30mg BD | SAC |
| 4.2. | Systemic PK | PK17 | Mean (+SD) CCI15106 Plasma Concentration-Time Plot (Linear and Semi-log) (Part 2) | For Part 2, 1) overlay day 1 and day 14 for each cohort (doses); 2) overlay all cohorts (doses) on same page for each full PK sampling day, Day 1 and Day 14 | SAC |
| 4.3. | Systemic PK | PK17 | Mean (+SD) CCI15106 Trough Plasma Concentration by study day (Linear and Semi-log) (Part 1 and Part 2) | Overlay the all cohorts on same page | SAC |
| 4.4. | Systemic PK | PK17 | Mean (+SD) CCI15106 Plasma Concentration-Time Plot by Cohort (to compare between HV and COPD) (Linear and Semilog) | 1) plot to overlay only data after 60mg SD (part 1 cohort A and part 2 cohort A) 2) plot to overlay data after 60mg BD (part 1 cohort B and part 2 cohort B), overlay all full PK sampling day (day 1 and day 14) as well as population on same page | SAC |
| 4.5. | Systemic PK | | Boxplot of pre-BAL plasma concentration by cohort (Linear and Semi-log) | Create a legend mentioning: Cohort B, Part 1 – Healthy Cohort B Part 2 - COPD | SAC |

| Pharm | Pharmacokinetic: Figures | | | | | | |
|---------|--------------------------|-------------------------|--|--|---------------------------|--|--|
| No. | Population | IDSL / Example Shell | Title | Programming Notes | Deliverable [Priority] | | |
| 4.6. | BAL PK | | Boxplot of Lung ELF CCI15106 concentration by cohort (Linear and Semi-log) | | SAC | | |
| Individ | ual Concentrati | on Plots | | | | | |
| 4.7. | Systemic PK | PK16a | Individual CCI15106 Plasma Concentration-Time Plot (Linear and Semi-log) (Part 1) | For Cohort A, overlay profiles after the 60mg, 120mg, and overlay profiles on day 1 and day 14 (after 30mg BD) on the same plot For Cohort B, overlay profiles on day 1 and day 14 on the same plot | SAC | | |
| 4.8. | Systemic PK | PK16a | Individual CCI15106 Plasma Concentration-Time Plot (Linear and Semi-log) (Part 2) | For Cohort B, also overlay profiles on day 1 and day 14 on the same plot (ignore pre-dose PK from day 2 to day 12, and day 15) | SAC | | |
| 4.9. | Systemic PK | Non-Standard PK_F1 | CCI15106 trough Plasma Concentration versus Study Day (Part 1 and Part 2) | Use line plot, All pre-dose from Day 2 following the BD regimens onwards Linear scale only | SAC | | |
| 4.10. | Systemic PK | Non-Standard PK_F1 | CCI15106 Plasma Concentration at follow up visit versus Subject ID (Part 1 and Part 2) | Scatter Plot | SAC | | |
| 4.11. | BAL PK | Non-Standard PK_F2 | Scatter Plot of Lung Drug Concentration versus Subject ID (Part 1 and Part 2) | X Axis: Subject ID Y-Axis: ELF Values | SAC | | |
| 4.12. | BAL PK | Non-Standard PK_F2 | Scatter Plot of Lung Drug Concentration versus Plasma Drug Concentration (BAL cohorts in Part 1 and Part 2) | data for all patients on same page separate colours for healthy and COPD patients Cohorts B for both parts The template is similar to PK_F2, only change the X-axis to plasma drug concentration. | SAC | | |

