8. PHARMACOKINETIC ANALYSES

8.1. Overview of Planned Pharmacokinetic Analyses

The PK analyses will be based on the "Systemic Pharmacokinetic Concentration" population for the plasma drug concentration data, and "BAL PK Population" for the lung ELF concentration data, unless otherwise specified.

Table 4 provides an overview of the planned analyses, with full details being presented in Appendix 11: List of Data Displays.

Table 4 Overview of Planned Pharmacokinetic Analyses

| Endpoints | | | Untr | ransfo | rmed | | | ormed | d | | | | | |
|------------------------------------|------|-------|-------|--------|-------------------|-----------------|------------|-------|----------------|-----------------|---|-----------------|------------|---|
| | Stat | s Ana | lysis | Sum | Summary | | Individual | | Stats Analysis | | | mary | Individual | |
| | T | F | L | T | F | F | L | Т | F | Ш | Т | F | F | L |
| Plasma Drug Concentrations | | | | Y | Y [1] [2] [3] [4] | Y [1] | Υ | | | | | Y [1] [2] | Y [1] | |
| Derived PK Parameters | Υ | | | Υ | | | Υ | Υ | Y [7] | Y [8] | | | | |
| Lung ELF CCI15106 Concentration | | | | Υ | Y [5] | Y [6] | Υ | | | | | | Y [1] | |

NOTES:

- T = Table, F = Figure, L = Listings, Y = Display generated.
- Stats Analysis = Represents TFL related to any formal statistical analyses (i.e. modelling) conducted.
- Summary = Represents TFL related to any summaries (i.e. descriptive statistics) of the observed raw data
- Individual = Represents FL related to any displays of individual participant observed raw data.
- 1. Linear and Semi-Log plots will be created on the same display.
- 2. Separate Mean (± SD) and Median plots will be generated, for the BD cohorts, overlay the day 1 and day 14 on same plot where possible.
- 3. Mean (± SD) and Median plots by cohorts a) to compare over the first 12hours for 60mg in HV (part 1) and COPD (part 2); b) to compare the 60mg SD (over 24h) HV vs COPD; c) to compare the 60mg BD HV vs COPD one for each of the intense sampling day (day 1, day 14).
- 4. Boxplot of plasma drug concentration at the follow up visit by cohort.
- 5. Boxplot of Lung CCI15106 concentration by cohort (HV vs COPD).
- 6. Lung CCI15106 concentration by Subject ID.
- 7. Dose proportionality of single and repeat dose and accumulation ratios from Cohorts A and B will be evaluated in Part 1 and Part 2.
- 8. Supportive SAS Output from Statistical Analysis of Loge-transformed Plasma PK Parameters.

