- 7. To be performed at the following timepoints in the mornings only: pre-dose, and 0.25 (in participants with COPD only), 0.5, 1, 4 h post-dose
- 8. To be performed at the following timepoints in the mornings only: pre-dose and 4 h post-dose

- 9. Telemetry may be performed on Days 11 or 12 instead, not to coincide with the BAL procedure.
- 10. ECG and vital signs to be obtained 2 h after the morning dose
- 11. When BAL is performed, vital signs and ECG will be performed before and after the procedure and oxygen saturation will be measured continuously.
- 12. For cohort with bystanders, BID doses may have ±1.5 h window.
- 13. PK samples on days 1 and 14 will be collected at the following timepoints: pre-dose, 0.25, 0.5, 0.75, 1, 2, 4, 6, 8, 10, 12 h. The evening dose will be given after 12 h post-dose sample is collected. On all other days, PK sample will be collected once, before the morning dose. When BAL is performed, one additional PK sample will be collected after dosing immediately prior to bronchoscopy
- 14. Done once during these four days, as soon as possible (within 1 h) after the first dose of the day
- 15. To be collected immediately before bronchoscopy

Schedule for Cohort C Part 1 (bystanders and air monitoring), to be executed concomitantly with Cohort B Part 1

| Procedure Treatment Period, Days | | | | | | | | | | | | | | | | |
|---|----------------|----------------|---|-----------------------|----|--------------------|-------------------|----------------|----|---|-----------------------|----|----|----|----------------|----|
| | -1 | 1 | 2 | 3 | 4 | 5 | 6 | 7 | 8 | 9 | 10 | 11 | 12 | 13 | 14 | 15 |
| Inclusion and exclusion criteria | X | | | | | | | | | | | | | | | |
| Brief physical examination, oral examination | X | | | | | | | | | | | | | | | Х |
| Substance testing (drugs, alcohol, tobacco) | Х | | | | | | | | | | | | | |] | |
| Serum pregnancy test in women | Х | | | | | | | | | | | | | | | |
| Admittance to clinic | X | | | | | | | | | | | | | | | |
| Discharge | | | | | | | | | | | | | | | | X1 |
| Training ² | X | | | | | | | | | | | | | | | |
| Haematology, clinical chem and urinalysis (include liver chem)3 | X | | | | | | | Χ | | | | | | | | Χ |
| Exposure to dosing | | Χ | Χ | X | Χ | X | X | X | Χ | X | Χ | X | X | X | Χ | |
| PK blood sample | | X ⁴ | | | | | | X ⁴ | | | | | | | X ⁴ | X |
| Stationary pump air monitoring ⁵ | | Χ | | | | | | Χ | | | | | | | Χ | |

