11.4.2. Reporting Standards

General

- The current GSK Integrated Data Standards Library (IDSL) will be applied for reporting, unless otherwise stated (IDSL Standards Location: https://spope.gsk.com/sites/IDSLLibrary/SitePages/Home.aspx):
 - 4.03 to 4.23: General Principles
 - 5.01 to 5.08: Principles Related to Data Listings
 - 6.01 to 6.11: Principles Related to Summary Tables
 - 7.01 to 7.13: Principles Related to Graphics

Formats

- All data will be reported according to the actual treatment the subject received unless otherwise stated.
- GSK IDSL Statistical Principles (5.03 & 6.06.3) for decimal places (DP's) will be adopted for reporting of data based on the raw data collected.
- Numeric data will be reported at the precision collected on the CRF.
- The reported precision from non CRF sources will follow the IDSL statistical principles but may be adjusted to a clinically interpretable number of DP's.

Planned and Actual Time

- Reporting for tables, figures and formal statistical analyses:
 - Planned time relative to dosing will be used in figures, summaries, statistical analyses and calculation of any derived parameters, unless otherwise stated.
 - The impact of any major deviation from the planned assessment times and/or scheduled visit days
 on the analyses and interpretation of the results will be assessed as appropriate.
- Reporting for Data Listings:
 - Planned and actual time relative to study drug dosing will be shown in listings (Refer to IDSL Statistical Principle 5.05.1).
 - Unscheduled or unplanned readings will be presented within the subject's listings.
 - Visits outside the protocol defined time-windows (i.e. recorded as protocol deviations) will be included in listings but omitted from figures, summaries and statistical analyses.

| Unscheduled Visits | | | | | | |
|---|--|--|--|--|--|--|
| Unscheduled visits | Unscheduled visits will not be included in summary tables. | | | | | |
| Unscheduled visits | Unscheduled visits will not be included in figures. | | | | | |
| All unscheduled visits will be included in listings. | | | | | | |
| Descriptive Summary Statistics | | | | | | |
| Continuous Data Refer to IDSL Statistical Principle 6.06.1 | | | | | | |
| Categorical Data N, n, frequency, % | | | | | | |
| Graphical Displays | | | | | | |
| Refer to IDSL Statistical Principals 7.01 to 7.13. and Standards for the Transfer and Reporting of PK Data using HARP | | | | | | |

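### The planned displays of lung ELF and pre-BAL plasma concentration leave out time since dose, so they cannot show whether a healthy-versus-COPD difference comes from sample timing

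*SAP*

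**What the plan says.** In the repeat-dose schedule (SAP 11.2.1), note 14 gives the timing of the lavage: "Done once during these four days, as soon as possible (within 1 h) after the first dose of the day". Note 13 gives that of the paired plasma sample: "one additional PK sample will be collected after dosing immediately prior to bronchoscopy". Both notes apply to the repeat-dose cohorts of Parts 1 and 2 alike, and neither sets a nominal post-dose time.

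The displays that use these samples (SAP 8.1, 11.10.6 and 11.10.7) are:

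- Table 4.3: ELF summary by cohort.
- Figure 4.5: boxplot of pre-BAL plasma, with a legend separating Cohort B Part 1 (healthy) from Cohort B Part 2 (COPD).
- Figure 4.6: boxplot of ELF by cohort. Note 5 to Table 4 gives the contrast intended: "Boxplot of Lung CCI15106 concentration by cohort (HV vs COPD".
- Figure 4.11: individual ELF values, "X Axis: Subject ID Y-Axis: ELF Values".
- Figure 4.12: ELF against plasma, with healthy and COPD in separate colours. The instruction is to reuse the Figure 4.11 template and "only change the X-axis to plasma drug concentration".

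On time in general, 11.4.2 says "Planned time relative to dosing will be used in figures, summaries, statistical analyses and calculation of any derived parameters, unless otherwise stated". Listings are to show both planned and actual time. Section 8.1.2.1 requires actual times for non-compartmental parameters, which do not include the single ELF values. Section 5 plans no covariates.

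**The concern.** Lung concentration is a secondary endpoint (SAP 2.2), and these descriptive displays are its only planned analysis. Healthy and COPD participants belong to different parts of the study, so randomisation does nothing to balance how soon after the dose each group is lavaged. With one value per person, the time of that value is part of its meaning.

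The plan itself treats the first hour as a period of change in plasma. On intensive days, four of the ten post-dose samples (0.25, 0.5, 0.75 and 1 h) fall in it, and the bystander endpoint in 2.2 puts the predicted plasma peak at 15-20 min. If one group is on average sampled later, the boxplots could show a gap that is not a population effect, or could mask one that is. None of the five displays would let the reader tell.

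**Working it through.** **Step 1. Does any planned display carry time since dose?**

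| Display | Grouping or axis | Time since dose |
|---|---|---|
| Table 4.3 | cohort | no |
| Figure 4.5 | cohort | no |
| Figure 4.6 | cohort | no |
| Figure 4.11 | Subject ID | no |
| Figure 4.12 | plasma concentration, colour by population | no |

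Actual time would appear only under the general listing rule in 11.4.2. Listing 68 covers plasma. An ELF listing is marked in Table 4 and promised at the end of 8.1.2.1, but none of Listings 68 to 77 in 11.10.9 is one.

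**Step 2. Possible size for ELF.** The SAP states no ELF half-life, so there is no plan figure to reproduce and a range is assumed. Suppose there is no population effect and ELF declines mono-exponentially with the same half-life h in everyone. Log concentration is then linear in time, and the ratio of geometric means depends only on the difference d in mean sampling time:

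ratio = exp(ln 2 × d / h) = 2^(d/h)

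For example, d = 0.5 h and h = 1 h give 2^0.5 = 1.41.

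| Assumed ELF half-life (h) | d = 0.5 h | d = 0.25 h |
|---|---|---|
| 0.5 | 2.00 | 1.41 |
| 1 | 1.41 | 1.19 |
| 2 | 1.19 | 1.09 |
| 4 | 1.09 | 1.04 |
| 8 | 1.04 | 1.02 |

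A mean difference of 0.5 h is half the permitted window, so the first column is a demanding case.

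**Step 3. Possible size for pre-BAL plasma.** A one-compartment curve is assumed, with C(t) proportional to exp(−ke·t) − exp(−ka·t) and ke = ln 2 / half-life. The absorption rate ka is solved from ln(ka/ke)/(ka − ke) = 0.29 h, the midpoint of 15-20 min. Concentration relative to the peak is then:

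| Assumed plasma half-life (h) | 5 min | 30 min | 60 min |
|---|---|---|---|
| 0.5 | 0.62 | 0.88 | 0.47 |
| 1 | 0.66 | 0.92 | 0.66 |
| 2 | 0.71 | 0.95 | 0.80 |
| 12 | 0.83 | 0.99 | 0.96 |

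This is a single-dose curve. Drug left from earlier twice-daily doses would flatten it, so the relative changes are upper values for the assumed half-lives. A short half-life makes the sampling minute matter, and a long one makes it matter little.

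**The case against.** The strongest reply is that the plan creates no imbalance. Both cohorts follow the same schedule, and its aim is a prompt lavage, with 1 h as the outer limit. A reader might infer that lavage times are spread freely over the hour, or that the healthy-versus-COPD comparison is biased. The SAP supports neither reading: bias needs an actual timing difference between cohorts, and nothing in the document predicts one. This stands. What remains is that the plan does not show or check the timing.

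Other points also carry weight:

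- The comparison is descriptive, and no hypothesis is tested (2.4).
- The 15-20 min figure is a plasma prediction quoted for the bystander endpoint. It says nothing about ELF.
- Contrasting single samples at 15 and 60 min would give 2^(45/h), with h in minutes: 2.83, 1.68, 1.30 and 1.14 for h = 30, 60, 120 and 240. These are differences between two individuals, not expected differences between cohorts.
- The planned-time rule is not the cause, because the five displays have no time axis. It matters only once such an axis is added.
- Subject ID is an ordinary axis for showing individual values and outliers, and is not an error in itself.
- Figure 4.12 pairs ELF with plasma drawn just before bronchoscopy, so each pair is closely matched in time. Time since dose can still vary between pairs.

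There are partial safeguards. Section 4 has ELF samples affected by protocol deviations reviewed for exclusion, and 11.4.2 omits out-of-window visits from figures and summaries. These can deal with late lavages, but not with variation inside the hour.

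**Conclusion.** The point holds as a gap in reporting. The samples have no nominal time, the cohorts compared are not randomised, and no planned table or figure carries the dose-to-sample interval. A timing difference, if one occurred, could not be told apart from a population difference.

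Its size cannot be fixed from the SAP. Under mono-exponential decline and assumed ELF half-lives of 0.5 to 8 h, the spurious ratio is 2.00 down to 1.04 for a 0.5 h shift in mean timing, and 1.41 down to 1.02 for 0.25 h. It therefore runs from negligible to about two-fold.

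A reader might also infer that the comparison needs adjustment by a model. That does not follow. There is one value per participant, the window is at most an hour, and concentrations may rise and then fall within it, so there is no obvious form for time and such a model would be fragile. Showing the times is enough, and it is a cheap improvement.

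**What to change.** - Derive the actual time from dose to BAL and from dose to pre-BAL plasma sample for each participant.
- Report median and range of these times by cohort with Table 4.3 and Figures 4.5 and 4.6.
- Plot ELF against actual time since dose in Figure 4.11, in place of or in addition to Subject ID. Plot pre-BAL plasma in the same way. Mark healthy and COPD participants separately in both.
- State in 11.4.2 that actual time is used for these BAL displays.
- Add the ELF listing promised in 8.1.2.1 to 11.10.9, with actual time since dose shown.

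The comparison stays descriptive, with no covariate model. The cost is SAP wording, one or two changed or extra displays, and the missing listing. The general listing rule already calls for actual times, so new data collection should not be needed, and the lavage schedule is untouched.

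A related but separate correction belongs in the same edit. Section 4 restricts the BAL PK population to healthy participants, while Figures 4.6, 4.11 and 4.12 use that population for displays that are meant to include COPD. These passages must be reconciled before the displays can be produced.
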